**Degree of correlation between *Disease State per EUS-FNA* and *Disease State per Consensus Board or per Histology*:**

- $[A+B+C+D+Y] / [\text{TOTAL}]$

**Diagnostic accuracy for Serous Cysts:**

- Sensitivity

$$= [A] / [A+K+L+N+Q]$$

- Specificity

$$= [B+C+D+H+I+J+M+O+P+R+S+T+V+W+X+Y] / [B+C+D+E+F+G+H+I+J+M+O+P+R+S+T+U+V+W+X+Y]$$

- Positive Predictive Value (PPV)

$$= [A] / [A+E+F+G+U]$$

- Negative Predictive Value (NPV)  

$$= [B+C+D+H+I+J+M+O+P+R+S+T+V+W+X+Y] / [B+C+D+H+I+J+K+L+M+N+O+P+Q+R+S+T+V+W+X+Y]$$
- Overall Accuracy  

$$= [A+ B+C+D+H+I+J+M+O+P+R+S+T+V+W+X+Y] / [TOTAL]$$

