- h. Accuracy of two EUS-FNA-based standard assays (cytology and CEA) as a diagnostic measure of disease state categorized as one of the following: *serous cyst, mucinous cyst, intra papillary mucinous neoplasm (IPMN), or pseudocyst*.

NOTES:

- Determination of disease state per EUS-FNA will be based on results from cytology and CEA and will follow published criteria.⁴ Definitions of the diagnostic accuracy measures are provided in **Appendix C.3**.
- Samples that do not have both diagnostic assay results (cytology and CEA) will be labeled as *Indeterminate*.

- i. Post EUS-FNA patient management plan (clinical and/or imaging surveillance, percutaneous aspiration, surgical removal).
- j. Impact of EUS-FNA based assays on diagnosis.
- k. Rate of cross-over to salvage.

5. Subject Selection

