8.3. Procedure

8.3.1. Lesion Characteristics

The following lesion characteristics will be assessed by EUS prior to the start of the FNA procedure and will be recorded on the *Procedure CRF*:

- a. Cyst size (maximal diameter, and cross-sectional diameter)

NOTE: In the case of a multilocular cyst, size will be measured both as the aggregate size of all cyst locules and the long and short perpendicular axis of the largest locule.

- b. Number of locules (1, 2, 3, 4, 5, 6-10, > 10)
- c. Presence of visible mucin (floating, or mobile filling defects)
- d. Presence of mural nodule (non-mobile filling defect) and size
- e. Presence of solid components
- f. Presence of distinct PCL wall
- g. Connectivity to pancreatic duct
- h. Maximal pancreatic duct diameter

An EUS image of the patient's PCL will be saved during the procedure.

8.3.2. *EUS-FNA Procedure*

The EUS-FNA procedure will be carried out in line with the guidelines provided in **Section 7** above, and the following data will be collected and recorded on the *Procedure CRF*:

- a. Route of access (gastric, duodenal, esophageal)
- b. Ease of insertion of EUS-FNA needle through echoendoscope
- c. Ability to reach target lesion
- d. Ability to penetrate into target lesion
- e. Quality of needle visualization
- f. Number of needle passes
- g. Ease of removal of EUS-FNA needle from echoendoscope
- h. Aspirate characteristics and adequacy of aspirate volume to perform two assays (cytology and CEA)
- i. Adverse Event assessment during procedure and through 2 Hours Post-Procedure or discharge from endoscopy unit

8.4. **Cytology and Chemistry Results**

The results of cyst aspirate cytology and CEA assessments will be provided by the cytology and chemistry labs and will be recorded on the *Cytology and Chemistry Results CRF*. Results will be categorized as follows⁴ and will be used for determination of Disease State per EUS-FNA:

- Cytology
 - Bland PAS +
 - Mucinous
 - Pigmented histiocytes
- CEA (ng/mL)
 - < 0.5
 - > 0.5 and < 200
 - > 200

8.5. **30-Day Follow-up**

The post-procedure 30-day Follow-up Visit will be conducted over the telephone. The visit window allows for this visit to occur anytime from 25 days to 35 days post procedure. Patients will be assessed for potential adverse events that might have occurred from discharge until 30 days post-procedure. AE information will be recorded on the *Adverse Event CRF*.

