#### 5.1.2 Diagnostic Accuracy Measures

Diagnostic accuracy is defined in terms of “disease state” and the following three disease state categories will be used in this study in order to assess diagnostic accuracy of EUS-FNA:

- “*Disease State per EUS-FNA*”: This measure is derived from the results of the cytology and chemistry assays of the cyst aspirate. Cysts will be classified as *serous cyst, mucinous cyst, IPMN, or pseudocyst* based on the table below. If any of the aspirate assays are not performed or the results from the two aspirate-based assays do not follow the table below, then the Disease State per EUS-FNA will be classified as

*Indeterminate.* The Disease State per EUS-FNA will be recorded on the *Cytology and Chemistry Results CRF*.

Disease State per EUS-FNA	Cytology	Cyst Fluid CEA (ng/mL)
Serous	Bland PAS +*	< 0.5
Mucinous	Mucinous	> 200
IPMN	Mucinous	> 200
Pseudocyst	Pigmented histiocytes	< 200

\* This cytological assay might be replaced by another cytological assay as needed

In order to assess the accuracy of EUS-FNA-based standard assays (cytology and CEA) as a diagnostic measure of disease state, the *Disease State per EUS-FNA* measure will be compared to a reference diagnosis. The reference diagnostic standard will be diagnosis from a surgical specimen histology, the true gold standard for cases that evolve to surgical resection within the 30 day follow-up time of the protocol. For cases that do not progress to surgery within 30 days of the EUS-FNA procedure, the reference diagnostic standard will be a composite diagnosis by a consensus board. The consensus board will consist of 3 to 5 Investigators who will be blinded to the type of needle used. The diagnosis of disease state will be based solely on baseline medical history and EUS and cross sectional imaging of the cyst. Information regarding aspirate characteristics and results from aspirate tests will not be provided to the consensus board. Diagnoses will be rendered at a separate Investigators Meeting or virtual meeting.

- “*Disease State per Histology*”: This is the reference diagnostic standard. This measure is derived from the histology results of the surgical specimen in cases that progress to surgery within 30 days. Cysts will be classified as follows: *serous cyst*, *mucinous cyst*, *IPMN*, *pseudocyst*, or *Indeterminate*. As described above, this measure will serve as the gold standard for assessing diagnostic accuracy.

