- “*Disease State per Consensus Board*”: This is the surrogate for the reference diagnostic standard. This measure is derived by the consensus board as described above. Cysts will be classified as follows: *serous cyst*, *mucinous cyst*, *IPMN*, *pseudocyst*, or *Indeterminate*. The classification will be based on baseline medical history and EUS and cross sectional imaging. Medical history will include, but not be limited to presence or absence of prior necrotizing pancreatitis, trauma or other potential cause of pseudocyst. Imaging will pertain to cyst location and cyst appearance.

**Degree of correlation between *Disease State per EUS-FNA* and *Disease State per Consensus Board or per Histology*** is illustrated below.

Total number of subjects enrolled is sum of all entries, namely

$$\text{TOTAL} = A + B + C + \dots + S + T + U + V + W + X + Y.$$

PCL Type	Serous per Consensus Board or Histology	Mucinous per Consensus Board or Histology	IPMN per Consensus Board or Histology	Pseudocyst Per Consensus Board or Histology	Indeterminate per Consensus Board or Histology
Serous per EUS-FNA	A	E	F	G	U
Mucinous per EUS-FNA	K	B	H	I	V
IPMN per EUS-FNA	L	M	C	J	W
Pseudocyst Per EUS-FNA	N	O	P	D	X
Indeterminate Per EUS-FNA	Q	R	S	T	Y

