#### Diagnostic accuracy for Mucinous Cysts:

- Sensitivity  

$$= [B] / [B+M+O+E+R]$$
- Specificity  

$$= [A+C+D+Y+F+G+J+L+N+P+Q+S+T+U+W+X] / [A+C+D+F+G+H+I+J+K+L+N+P+Q+S+T+U+W+X+Y+V]$$
- Positive Predictive Value (PPV)  

$$= [B] / [B+H+I+K+V]$$
- Negative Predictive Value (NPV)  

$$= [A+C+D+F+G+J+L+N+P+Q+S+T+Y+U+W+X] / [A+C+D+E+F+G+J+L+M+N+O+P+Q+R+S+T+U+W+X+Y]$$
- Overall Accuracy  

$$= [A+B+C+D+F+G+J+L+N+P+Q+S+T+U+W+X+Y] / TOTAL$$

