#### Diagnostic accuracy for IPMN:

- Sensitivity  

$$= [C] / [C+F+H+P+S]$$
- Specificity  

$$= [A+B+D+E+G+I+K+N+O+Q+R+T+U+V+W+X+Y] / [A+B+D+E+G+I+J+K+L+M+N+O+Q+R+T+U+V+W+X+Y+W]$$
- Positive Predictive Value (PPV)  

$$= [C] / [C+J+L+M+W]$$
- Negative Predictive Value (NPV)  

$$= [A+B+D+E+G+I+K+N+O+Q+R+T+U+V+W+X+Y] / [A+B+D+E+F+G+H+I+K+N+O+P+Q+R+S+T+U+V+W+X+Y]$$
- Overall Accuracy  

$$= [A+B+C+D+E+G+I+K+N+O+Q+R+T+U+V+W+X+Y] / TOTAL$$

**Diagnostic accuracy for Pseudocysts (in principle excluded from study, but a few cases may not have been identified at baseline as such):**

- Sensitivity  
=  $[D] / [D+G+I+J+T]$
- Specificity  
=  $[A+B+C+E+F+H+K+L+M+Q+R+S+U+V+W+Y] / [A+B+C+E+F+H+K+L+M+N+O+P+Q+R+S+U+V+W+Y+X]$
- Positive Predictive Value (PPV)  
=  $[D] / [D+N+O+P+X]$
- Negative Predictive Value (NPV)  
=  $[A+B+C+E+F+H+K+L+M+Q+R+S+U+V+W+Y] / [A+B+C+E+F+G+H+I+J+K+L+M+Q+R+S+T+U+V+W+Y+X]$
- Overall Accuracy  
=  $[A+B+C+D+E+F+H+K+L+M+Q+R+S+U+V+W+Y] / \text{TOTAL}$

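### The diagnostic-accuracy formulas treat an Indeterminate EUS-FNA result as test-negative, so specificity by arm rises as needle yield falls whenever classified results include false positives

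*SAP*

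**What the plan says.** Endpoint h is the accuracy of cytology and CEA as a measure of disease state, and diagnostic accuracy by needle is part of the stated primary objective. The rule for the EUS-FNA state is in SAP 5.1.2 and Protocol C.3: "If any of the aspirate assays are not performed or the results from the two aspirate-based assays do not follow the table below", the state is Indeterminate. The note to endpoint h in Protocol 4.2 agrees on the first half: "Samples that do not have both diagnostic assay results (cytology and CEA) will be labeled as" Indeterminate.

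Both documents then cross the EUS-FNA state with the reference state in a 5×5 table. In the SAP's words, "Total number of subjects enrolled is sum of all entries, namely" A through Y. The Indeterminate-per-EUS-FNA row is Q, R, S, T, Y. The Indeterminate-reference column is U, V, W, X, Y.

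The specificity numerators in the SAP are:

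- serous: "B+C+D+H+I+J+M+O+P+R+S+T+V+W+X+Y"
- mucinous: "A+C+D+Y+F+G+J+L+N+P+Q+S+T+U+W+X"
- IPMN: "A+B+D+E+G+I+K+N+O+Q+R+T+U+V+W+X+Y"
- pseudocyst: "A+B+C+E+F+H+K+L+M+Q+R+S+U+V+W+Y"

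Overall agreement is A, B, C, D and Y over the total. SAP 4.1 analyses all endpoints by randomization arm in the ITT set. Neither document plans these measures on classified samples only.

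**The concern.** An Indeterminate result here is not evidence that a cyst is of another type. It means that no usable result was obtained, or that the pair of results fits no row. Counting it as a correct negative for every non-target class makes specificity depend on how often the needle fails to deliver a classifiable sample. The trial expects yield to differ between needles, so a comparison of specificity by arm would partly be a comparison of failure rates, with its sign reversed.

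Two related choices have the same character. Y, where neither the test nor the reference reached a diagnosis, counts as agreement. U to Y, where the reference is unknown, are all placed in the non-disease group of every class.

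**Working it through.** **Inputs.** The cell layout and formulas are from SAP 5.1.2 and Protocol C.3. The planning success rates for endpoint c, 75% for 22 G and 19 G and 91% for 19 G Flex, are from SAP 3.2.2 and Protocol C.2. The false-positive rate φ among classified non-target cysts, the sensitivity Se among classified target cysts, and prevalence are assumptions. The documents state no accuracy figure, so there is none to reproduce.

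**Step 1: where the Indeterminate row goes.** For each class I derived the one-versus-rest cells and compared them with every formula.

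| Class | Miss in sensitivity | Credited in specificity, NPV and accuracy numerators |
|---|---|---|
| Serous | Q | R, S, T, Y |
| Mucinous | R | Q, S, T, Y |
| IPMN | S | Q, R, T, Y |
| Pseudocyst | T | Q, R, S, Y |

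This holds in both documents. Two cells depart from the one-versus-rest pattern:

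- W is IPMN per EUS-FNA, so it is a test positive. The SAP's IPMN formulas put it in the specificity, NPV and accuracy numerators and in the NPV denominator, and list it twice in the specificity denominator. Protocol C.3 does none of this.
- X is pseudocyst per EUS-FNA. It stands in the pseudocyst NPV denominator in both documents.

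**Step 2: what the table classifies.** Protocol 8.4 lists three cytology categories (bland PAS+, mucinous, "Pigmented histiocytes") and three CEA bands, giving 9 pairs. One is serous, one satisfies both the mucinous and the IPMN row, and two are pseudocyst. The other 5 are Indeterminate. This counts category pairs, not patients.

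**Step 3: specificity.** Let f be the Indeterminate share, taken as unrelated to the reference class. Of the non-target cysts, f are credited as negative and (1 − f)φ are false positives, so

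specificity = 1 − (1 − f)φ.

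(For IPMN this describes the Protocol formula; the SAP version is disturbed further by W.) Take f = 1 − 0.91 = 0.09 and f = 1 − 0.75 = 0.25. The gap is (0.25 − 0.09)φ = 0.16φ.

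| φ (assumed) | f = 0.09 | f = 0.25 | Gap, points |
|---|---|---|---|
| 0 | 100% | 100% | 0 |
| 0.05 | 95.45% | 96.25% | 0.8 |
| 0.10 | 90.9% | 92.5% | 1.6 |
| 0.20 | 81.8% | 85.0% | 3.2 |
| 0.30 | 72.7% | 77.5% | 4.8 |

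On classified samples only, specificity is 1 − φ in both arms, whatever f is.

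**Step 4: sensitivity.** The formulas give (1 − f)Se. At Se = 0.80 this is 0.91 × 0.80 = 72.8% against 0.75 × 0.80 = 60.0%, a difference of 12.8 points in favour of the higher-yield needle.

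**Step 5: overall accuracy.** With prevalence π, accuracy = (1 − π) + (1 − f)[πSe − (1 − π)φ]. At Se = 0.80 and φ = 0.20 the bracket is zero at π = 0.20. Above that, accuracy rewards yield; below it, accuracy rewards non-yield. At an assumed π = 0.05 the bracket is 0.04 − 0.19 = −0.15. Accuracy is then 0.95 − 0.91 × 0.15 = 81.35% at f = 0.09 and 0.95 − 0.75 × 0.15 = 83.75% at f = 0.25.

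**Step 6: the limit.** A needle with no yield (f = 1) would show 100% specificity and 0% sensitivity for every class, an undefined PPV, and NPV and accuracy both equal to 1 − π.

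**The case against.** The best defence is that the formulas follow one consistent convention: whatever is not positive for the class is negative. The patients credited in specificity for one class are penalised in sensitivity for another, and at the values above the sensitivity loss is larger than the specificity gain. Endpoint h carries no hypothesis or power, and SAP 5.1.1 plans descriptive summaries only. The 5×5 table shows the Indeterminate row openly. The per-protocol set requires an aspirate volume above zero.

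Much of this is fair and limits the consequences, but it does not remove the problem. A reader would see a sensitivity/specificity trade-off between needles that is nothing but yield. The per-protocol set removes only the Indeterminate samples that had no aspirate. Under Protocol 7.4 an aspirate below 1 cc goes to cytology; if CEA is then not done, the sample is Indeterminate but stays per-protocol, as do off-table pairs. The SAP 7.4 rule on non-missing denominators does not help either, because Indeterminate is a recorded category inside the total.

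Some stronger readings are tempting but unsupported:

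- A reader might infer that most patients will be Indeterminate. The documents give no frequencies; 5 of 9 is a count of pairs.
- A reader might infer that every failed aspiration is Indeterminate. Protocol 7.2 also calls a procedure failed on residual diameter, and such a case can still have both assays. The documents do not say whether salvage aspirate may supply them.
- A reader might take 3.2 points as the expected bias. It rests on an assumed φ and on endpoint c success, which is met by cyst collapse or adequate fluid. Neither guarantees an on-table pair.
- A reader might want Indeterminate scored as incorrect in specificity. That gives (1 − f)(1 − φ) = 72.8% against 60.0% at φ = 0.20 for two equally accurate needles, a larger distortion in the opposite direction.

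**Conclusion.** The point holds. In both documents and all four classes, Indeterminate per EUS-FNA is handled as test-negative, so ITT specificity by arm rises with non-yield whenever φ exceeds zero. The size is the difference in Indeterminate share times φ: 0.8 to 4.8 points for φ from 0.05 to 0.30 at the proxy shares, and nothing at φ = 0. It comes with an opposite movement in sensitivity. This assumes equal true accuracy across needles and an Indeterminate share unrelated to cyst type. The documents do not support a claim that the lower-yield needle would look better overall; the supported claim is that the measures mix yield with accuracy. The misplacement of W (SAP only) and X (both documents) is a plain formula error that needs no assumptions. The primary endpoint and endpoint c are not affected.

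**What to change.** In SAP 5.1.2 and Protocol C.3:

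1. As the main by-arm analysis, compute sensitivity, specificity, PPV, NPV and overall accuracy on samples with a determinate EUS-FNA class and a determinate reference. Serous specificity, for example, becomes [B+C+D+H+I+J+M+O+P] / [B+C+D+E+F+G+H+I+J+M+O+P]. Report the Indeterminate proportion by arm beside these measures. The present convention may stay as a labelled supplement.
2. Drop Y from the agreement numerator.
3. Leave U to Y out of the 2×2 measures and report their count.
4. Wherever the present formulas are kept, remove W from the SAP's IPMN specificity, NPV and accuracy numerators and from the NPV denominator, list it once in the specificity denominator, and remove X from the pseudocyst NPV denominator in both documents.

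The cost is formula and table edits, with no new data. Denominators become smaller and some figures less favourable. Classified subsets may also differ in case mix between arms, which is why the Indeterminate share must be shown alongside.

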#### Diagnostic accuracy for Mucinous Cysts:

- Sensitivity  

$$= [B] / [B+M+O+E+R]$$
- Specificity  

$$= [A+C+D+Y+F+G+J+L+N+P+Q+S+T+U+W+X] / [A+C+D+F+G+H+I+J+K+L+N+P+Q+S+T+U+W+X+Y+V]$$
- Positive Predictive Value (PPV)  

$$= [B] / [B+H+I+K+V]$$
- Negative Predictive Value (NPV)  

$$= [A+C+D+F+G+J+L+N+P+Q+S+T+Y+U+W+X] / [A+C+D+E+F+G+J+L+M+N+O+P+Q+R+S+T+U+W+X+Y]$$
- Overall Accuracy  

$$= [A+B+C+D+F+G+J+L+N+P+Q+S+T+U+W+X+Y] / TOTAL$$

#### Diagnostic accuracy for IPMN:

- Sensitivity  

$$= [C] / [C+F+H+P+S]$$
- Specificity  

$$= [A+B+D+E+G+I+K+N+O+Q+R+T+U+V+W+X+Y] / [A+B+D+E+G+I+J+K+L+M+N+O+Q+R+T+U+V+W+X+Y+W]$$
- Positive Predictive Value (PPV)  

$$= [C] / [C+J+L+M+W]$$
- Negative Predictive Value (NPV)  

$$= [A+B+D+E+G+I+K+N+O+Q+R+T+U+V+W+X+Y] / [A+B+D+E+F+G+H+I+K+N+O+P+Q+R+S+T+U+V+W+X+Y]$$
- Overall Accuracy  

$$= [A+B+C+D+E+G+I+K+N+O+Q+R+T+U+V+W+X+Y] / TOTAL$$

**Diagnostic accuracy for Pseudocysts (in principle excluded from study, but a few cases may not have been identified at baseline as such):**

- Sensitivity  
=  $[D] / [D+G+I+J+T]$
- Specificity  
=  $[A+B+C+E+F+H+K+L+M+Q+R+S+U+V+W+Y] / [A+B+C+E+F+H+K+L+M+N+O+P+Q+R+S+U+V+W+Y+X]$
- Positive Predictive Value (PPV)  
=  $[D] / [D+N+O+P+X]$
- Negative Predictive Value (NPV)  
=  $[A+B+C+E+F+H+K+L+M+Q+R+S+U+V+W+Y] / [A+B+C+E+F+G+H+I+J+K+L+M+Q+R+S+T+U+V+W+Y+X]$
- Overall Accuracy  
=  $[A+B+C+D+E+F+H+K+L+M+Q+R+S+U+V+W+Y] / \text{TOTAL}$

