PCL Type	Serous per Consensus Board or Histology	Mucinous per Consensus Board or Histology	IPMN per Consensus Board or Histology	Pseudocyst Per Consensus Board or Histology	Indeterminate per Consensus Board or Histology
Serous per EUS-FNA	A	E	F	G	U
Mucinous per EUS-FNA	K	B	H	I	V
IPMN per EUS-FNA	L	M	C	J	W
Pseudocyst Per EUS-FNA	N	O	P	D	X
Indeterminate Per EUS-FNA	Q	R	S	T	Y

Degree of correlation between *Disease State per EUS-FNA* and *Disease State per Consensus Board or per Histology*:

- $[A+B+C+D+Y] / [TOTAL]$

Diagnostic accuracy for Serous Cysts:

- Sensitivity
 $= [A] / [A+K+L+N+Q]$
- Specificity
 $= [B+C+D+H+I+J+M+O+P+R+S+T+V+W+X+Y] / [B+C+D+E+F+G+H+I+J+M+O+P+R+S+T+U+V+W+X+Y]$
- Positive Predictive Value (PPV)
 $= [A] / [A+E+F+G+U]$
- Negative Predictive Value (NPV)
 $= [B+C+D+H+I+J+M+O+P+R+S+T+V+W+X+Y] / [B+C+D+H+I+J+K+L+M+N+O+P+Q+R+S+T+V+W+X+Y]$
- Overall Accuracy
 $= [A+ B+C+D+H+I+J+M+O+P+R+S+T+V+W+X+Y] / [TOTAL]$

Diagnostic accuracy for Mucinous Cysts:

- Sensitivity
 $= [B] / [B+M+O+E+R]$
- Specificity
 $= [A+C+D+Y+F+G+J+L+N+P+Q+S+T+U+W+X] / [A+C+D+F+G+H+I+J+K+L+N+P+Q+S+T+U+W+X+Y+V]$
- Positive Predictive Value (PPV)
 $= [B] / [B+H+I+K+V]$
- Negative Predictive Value (NPV)
 $= [A+C+D+F+G+J+L+N+P+Q+S+T+Y+U+W+X] / [A+C+D+E+F+G+J+L+M+N+O+P+Q+R+S+T+U+W+X+Y]$
- Overall Accuracy
 $= [A+B+C+D+F+G+J+L+N+P+Q+S+T+U+W+X+Y] / TOTAL$

Diagnostic accuracy for IPMN:

- Sensitivity
 $= [C] / [C+F+H+P+S]$
- Specificity

$$= [A+B+D+E+G+I+K+N+O+Q+R+T+U+V+X+Y] / [A+B+D+E+G+I+J+K+L+M+N+O+Q+R+T+U+V+X+Y+W]$$

- Positive Predictive Value (PPV)
 $= [C] / [C+J+L+M+W]$
- Negative Predictive Value (NPV)
 $= [A+B+D+E+G+I+K+N+O+Q+R+T+U+V+X+Y] / [A+B+D+E+F+G+H+I+K+N+O+P+Q+R+S+T+U+V+X+Y]$
- Overall Accuracy
 $= [A+B+C+D+E+G+I+K+N+O+Q+R+T+U+V+X+Y] / \text{TOTAL}$

Diagnostic accuracy for Pseudocysts (in principle excluded from study, but a few cases may not have been identified at baseline as such):

- Sensitivity
 $= [D] / [D+G+I+J+T]$
- Specificity
 $= [A+B+C+E+F+H+K+L+M+Q+R+S+U+V+W+Y] / [A+B+C+E+F+H+K+L+M+N+O+P+Q+R+S+U+V+W+Y+X]$
- Positive Predictive Value (PPV)
 $= [D] / [D+N+O+P+X]$
- Negative Predictive Value (NPV)
 $= [A+B+C+E+F+H+K+L+M+Q+R+S+U+V+W+Y] / [A+B+C+E+F+G+H+I+J+K+L+M+Q+R+S+T+U+V+W+Y+X]$
- Overall Accuracy
 $= [A+B+C+D+E+F+H+K+L+M+Q+R+S+U+V+W+Y] / \text{TOTAL}$

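### The SAP's IPMN formulas count cell W, an IPMN false positive, as a true negative and list it twice in the specificity denominator, so IPMN specificity, NPV and accuracy are wrong and differ from the protocol

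*SAP*

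**What the plan says.** Both documents cross-classify the disease state from EUS-FNA (rows) against the reference diagnosis (columns) in the same 25-cell table (SAP 5.1.2; Protocol Appendix C.3). The IPMN row reads "IPMN per EUS-FNA L M C J W", and its last column is headed "Indeterminate per Consensus Board or Histology". TOTAL is the sum of all 25 cells.

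For IPMN, the SAP then gives:

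- Specificity: "A+B+D+E+G+I+K+N+O+Q+R+T+U+V+W+X+Y] / [A+B+D+E+G+I+J+K+L+M+N+O+Q+R+T+U+V+W+X+Y+W"
- NPV: "A+B+D+E+G+I+K+N+O+Q+R+T+U+V+W+X+Y] / [A+B+D+E+F+G+H+I+K+N+O+P+Q+R+S+T+U+V+W+X+Y"
- Overall accuracy: "A+B+C+D+E+G+I+K+N+O+Q+R+T+U+V+W+X+Y] / TOTAL"
- PPV: C divided by the whole IPMN row, so W is in the denominator only.

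The protocol's IPMN specificity is "A+B+D+E+G+I+K+N+O+Q+R+T+U+V+X+Y] / [A+B+D+E+G+I+J+K+L+M+N+O+Q+R+T+U+V+X+Y+W" and its NPV is "A+B+D+E+G+I+K+N+O+Q+R+T+U+V+X+Y] / [A+B+D+E+F+G+H+I+K+N+O+P+Q+R+S+T+U+V+X+Y". Its accuracy numerator has no W. Sensitivity and PPV are the same in both documents.

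**The concern.** A subject in W has a positive EUS-FNA call for IPMN that the reference does not confirm. The SAP's PPV line scores that subject as a false positive, while its specificity, NPV and accuracy lines score the same subject as a true negative. NPV should contain only test-negative subjects, and W is not test-negative. The specificity denominator should count each reference-non-IPMN subject once, but it counts W twice.

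Diagnostic accuracy by disease state is secondary endpoint h. SAP 7.2 has results produced by program without manual editing, so a formula coded as printed goes straight into the tables. The error always favours the test. In an arm with its own W and TOTAL, accuracy is overstated by that arm's W/TOTAL, so the distortion can also differ between arms.

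**Working it through.** **Step 1. Classify the cells for IPMN from the 25-cell table.** Test-positive is the IPMN row (L, M, C, J, W). Reference-positive is the IPMN column (F, H, C, P, S).

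- TP = C
- FP = J + L + M + W
- FN = F + H + P + S
- TN = the other 16 cells: A, B, D, E, G, I, K, N, O, Q, R, T, U, V, X, Y

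W is not in TN.

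**Step 2. Compare every printed formula with these sets.**

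| IPMN measure | From the table | Protocol C.3 | SAP 5.1.2 |
|---|---|---|---|
| Sensitivity | TP/(TP+FN) | agrees | agrees |
| PPV | TP/(TP+FP) | agrees | agrees |
| Specificity | TN/(TN+FP) | agrees | one extra W above, one extra W below |
| NPV | TN/(TN+FN) | agrees | one extra W above, one extra W below |
| Accuracy | (TP+TN)/TOTAL | agrees | one extra W above |

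The same comparison reproduces all serous and mucinous formulas in both documents. There the corresponding cells, U for serous and V for mucinous, are correctly handled as false positives.

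**Step 3. Size of the error in general.** Write f = J + L + M.

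- Accuracy: the SAP value minus the correct value is W/TOTAL.
- Specificity: (TN+W)/(TN+f+2W) − TN/(TN+f+W) = W(f+W) / [(TN+f+W)(TN+f+2W)], which is positive whenever W > 0.
- NPV: (TN+W)/(TN+FN+W) − TN/(TN+FN) = W·FN / [(TN+FN)(TN+FN+W)], which is positive whenever W > 0 and FN > 0.

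**Step 4. Example (assumed counts; the documents give none).** Take C = 40, f = 10, W = 12, FN = 30 and TN = 148. The sum is 40+10+12+30+148 = 240.

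| Measure | Correct | SAP |
|---|---|---|
| Accuracy | (40+148)/240 = 188/240 = 78.3% | (40+148+12)/240 = 200/240 = 83.3% |
| Specificity | 148/(148+10+12) = 148/170 = 87.1% | 160/(148+10+24) = 160/182 = 87.9% |
| NPV | 148/(148+30) = 148/178 = 83.1% | 160/(148+30+12) = 160/190 = 84.2% |

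The internal contradiction is visible in the counts. The false positives in the SAP's PPV line plus its other three groups add to 40+22+30+160 = 252, which is TOTAL + W and not 240.

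**Step 5. Range over W.** Assume 250 subjects, with those not in W spread evenly over the other 24 cells. This is an illustration, not a forecast. Each entry is correct → SAP.

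| W | Specificity | NPV | Accuracy |
|---|---|---|---|
| 0 | 0.842 → 0.842 | 0.800 → 0.800 | 0.708 → 0.708 |
| 5 | 0.821 → 0.825 | 0.800 → 0.805 | 0.694 → 0.714 |
| 10 | 0.800 → 0.810 | 0.800 → 0.810 | 0.680 → 0.720 |
| 20 | 0.759 → 0.780 | 0.800 → 0.819 | 0.652 → 0.732 |
| 40 | 0.679 → 0.731 | 0.800 → 0.837 | 0.595 → 0.755 |

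As W grows, correct accuracy falls while the SAP's version rises.

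**The case against.** The algebra is not in dispute. The strongest points on the other side concern origin and weight.

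- **Possible reading or retyping slip.** All five errors are the same change: a W inserted between V and X, within one block. They could have a single cause and are not five independent confirmations. The text was read from PDF by a program, so a look at the printed SAP page is sensible. But the insertion recurs in all five places, and the mucinous block has no matching insertion of V. A retyping slip by the SAP's author would still be an error in the SAP.
- **Limited reach.** SAP 5.1.1 summarises the secondary endpoints descriptively, and endpoint h has no hypothesis or power statement. The two tested endpoints are untouched. The accuracy part of the primary objective concerns mucinous versus non-mucinous cysts, which this block does not address directly. All of this stands, and it limits the consequence.
- **Unknown size.** The effect is zero if W = 0, and no document predicts W. That is right. But W can be non-zero by design: the consensus board may return an indeterminate diagnosis and does not see the aspirate results.
- **The validation step may catch it.** A letter listed twice in one sum is conspicuous. But validation that checks programs against the SAP would confirm the formula as printed.
- **A more basic problem.** The classification table gives mucinous cysts and IPMN identical cytology and CEA criteria, so how a case enters the IPMN row is undefined. This is a separate defect. Correcting W does not resolve it, and it does not excuse the formulas.

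**Conclusion.** The concern holds. As printed, the SAP's formulas for IPMN specificity, NPV and overall accuracy are wrong. They contradict the SAP's own PPV line and differ from Protocol Appendix C.3, which is correct for IPMN. Nothing in the SAP announces a changed definition, and no convention for indeterminate cases counts a subject twice in one denominator.

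Accuracy is overstated by exactly W/TOTAL. In the assumed 240-subject table with W = 12 that is 5.0 percentage points (12/240), against about 0.9 points for specificity (264/30,940) and 1.1 for NPV (360/33,820). The sizes rest on assumed cell counts; the direction does not. The error is confined to a descriptive secondary endpoint, but a program following the SAP would report wrong values for it whenever W > 0, so it must be corrected before the tables are programmed.

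**What to change.** In SAP 5.1.2, IPMN block:

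1. Remove W from the specificity numerator, and keep it once in the specificity denominator.
2. Remove W from both parts of NPV.
3. Remove W from the overall-accuracy numerator.

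The block then matches Protocol Appendix C.3.

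Add a programming check for each disease state that TP + FP + FN + TN equals TOTAL, and that each denominator equals its table margin: the reference column for sensitivity, all other columns for specificity, the EUS-FNA row for PPV, all other rows for NPV. The margin check is needed as well as the total. It would also catch a separate slip in both documents, where the pseudocyst NPV denominator includes X, a pseudocyst false positive.

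The cost is an SAP erratum and a short check in the code. No data collection, design or sample size changes. Where W > 0, the reported IPMN accuracy and specificity will be lower than under the SAP as printed, and so will NPV if there are any false negatives.
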